Wording was clarified for the schedule of follow up visits and procedures for subjects with PTH-specific antibodies at the final 2 visits (rather than the final visit).	Low levels of detectable antibody tend to be variable and of no known clinical significance.	Table 6-3, Table 6-4
Wording was added to clarify that additional interim analyses may be performed as necessary to support regulatory interactions and/or publications.	Updated information.	Section 8.6.3
Removed ( $\geq 7.5$ mg/dL) from the baseline value of albumin-corrected total serum calcium concentration since this was an inadvertent carryover from the previous study, REPLACE. Sentence now reads: An albumin-corrected total serum calcium concentration that is normalized or maintained compared to the baseline value ( <del><math>\geq 7.5</math> mg/dL</del> ) and does not exceed the ULN for the central laboratory	Correction.	Synopsis, Section 2.3.2, Section 8.3

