4.3. Other Efficacy Endpoints

- Mean percentage changes from baseline in supplemental oral calcium and supplemental calcitriol dosages at each visit
- Proportion of subjects achieving the three conditions of the efficacy endpoint defined above at each visit
- Mean change from baseline in 24-hour urine calcium excretion
- Impact of calcium source (carbonate vs. citrate) on response
- Impact of calcium-sparing diuretics on serum and urinary calcium
- Proportion of subjects that maintain a calcium phosphate product in the range of 35 to 55 mg^2/dL^2
- Distribution of subjects by rhPTH[1-84] doses at the End of Treatment Visit
- Change from baseline in bone turnover markers, bone-specific alkaline phosphatase, serum carboxy-terminal telopeptide of type I collagen, serum procollagen type I amino-terminal propeptide, osteocalcin, PTH antibodies, and BMD by DXA
- Additional subgroup analyses that are specified in the SAP

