5.1. General Methodology

All statistical procedures will be completed using SAS version 9.4¹. No formal statistical testing will be conducted for this study. Summary statistics will be provided.

Continuous variables, including those assessed on a discrete scale, will be summarized using descriptive statistics including number of subjects, mean, median, standard deviation, maximum, and minimum. For categorical variables, statistical summaries will include number of subjects and percentages.

For summary purposes, baseline will be defined as the last available pre-dose value, unless otherwise specified. End of treatment (EOT) time point, defined as the last determination of response or last available measurement during the treatment period (from the date of first dose to the date of last dose + 1 day), will be analyzed in addition to the scheduled visits. Visits will be summarized based on the analysis visit windows.

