6.7.2. Other Analyses

Mean percentage changes from baseline in supplemental oral calcium and supplemental calcitriol dosage at each visit

The absolute and percentage changes from baseline will be summarized at each visit. No formal statistical test will be done.

Proportion of subjects achieving the primary endpoint at each visit

The number and percentage of subjects achieving the primary efficacy endpoint will be presented by visit. No formal statistical test will be done.

Mean percentage change from baseline in 24-hour urine calcium excretion

The absolute and percentage changes from baseline will be summarized by visit. No formal statistical test will be done.

Impact of calcium source (carbonate vs. citrate) on response

The number and percentage of subjects meeting the criteria of being responders will be presented by visit and by calcium source (carbonate vs. citrate). No formal statistical test will be done.

Impact of calcium-sparing diuretics on serum and urinary calcium

The number and percentage of subjects who use at least one calcium-sparing diuretics during the study will be presented.

The urinary calcium will be listed for subjects who received calcium-sparing diuretics during the study. No formal statistical test will be done.

Proportion of subjects that maintain a calcium phosphate product in the range of 35 to 55 mg²/dL²

Calcium phosphate product will be classified as normal (35 - 55 mg²/dL²), or abnormal (including low and high). The number and percentage of subjects with maintenance of a calcium phosphate product in the normal range will be presented by visit. No formal statistical test will be done.

Distribution of subjects by rhPTH[1-84] doses at the End of Treatment Visit

The number and percentage of subjects at different dose levels at the EOT visit will be summarized. No formal statistical test will be done.

Change from baseline in bone turnover markers (bone-specific alkaline phosphatase, serum carboxy-terminal telopeptide of type I collagen, serum procollagen type I amino-terminal propeptide, and osteocalcin), PTH and ECP antibodies, and BMD by DXA

The absolute and percentage changes from baseline will be summarized by visit. No formal statistical test will be done. For DEXA, Z-scores will also be presented and summarized.

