6.8.4.5. PTH and ECP Antibodies

The number and percentage of subjects classified as having antibodies to PTH and ECP at baseline, Visit 5 (Week 24), Visit 7 (Week 40), and EOT will be tabulated for each treatment group.

If any subject tests positive for PTH-specific antibodies at the final visit, they will have follow-up blood draws for PTH antibody analysis at Months 2, 3, and 6 post-study. If a subject's results are negative at 2 successive visits within this timeframe, follow-up may be terminated. If at the end of 6 months the subject is still determined to have PTH-specific antibodies, the investigator and the sponsor will determine if additional follow-up may be required. During this time, subjects also will be evaluated for AEs or SAEs related to immunogenicity, which will be collected in the Pharmacovigilance database.

Subjects may remain on study if they develop PTH-specific antibodies during the study, providing that there are no concurrent AEs related to immunogenicity.

The number and percentage of subjects classified as having antibodies to PTH during the follow up period will also be provided, if applicable.

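### SAP 6.7.2 summarizes antibodies by change and percentage change from baseline, which does not fit a positive/negative result, and the n (%) table in SAP 6.8.4.5 omits Week 52 and the extension draws

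*SAP*

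**What the plan says.** SAP 6.7.2 has one heading covering the bone turnover markers, "PTH and ECP antibodies, and BMD by DXA". The rule for the whole group is "The absolute and percentage changes from baseline will be summarized by visit". DXA then gets an added provision for Z-scores; antibodies get none. SAP 4.3 lists the endpoint as change from baseline in PTH antibodies ("osteocalcin, PTH antibodies, and BMD by DXA"), so ECP enters this analysis only in 6.7.2.

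The safety part of the SAP handles the same assays differently. SAP 6.8.4.5 plans "The number and percentage of subjects classified as having antibodies to PTH and ECP at baseline", with the remaining time points given as "Visit 5 (Week 24), Visit 7 (Week 40), and EOT will be tabulated for each treatment group". It adds a count of subjects with PTH antibodies during post-study follow-up, if applicable. Protocol 6.2 and 6.4.9 also speak only of positive and negative results. The SAP's general rule in 5.1 is: "For categorical variables, statistical summaries will include number of subjects and percentages".

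On sampling, Protocol 6.2.3 schedules antibody draws at baseline, Weeks 24, 40 and 52, every 6 months in the extension, and at the End of Treatment visit.

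**The concern.** A change score needs a numerical scale, and a percentage change also needs a non-zero baseline. The documents describe neither for antibodies. A programmer following 6.7.2 must invent a value for a negative result, and the output depends on that choice.

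What is at stake is the long-term immunogenicity picture. The primary objective is long-term safety and tolerability, Protocol 2.3.1 lists immunogenicity among the safety endpoints, and Amendment 6 extended the study to collect more long-term safety data. The useful question is how many subjects who started negative became positive, and when. For the draws at Week 52 and in the extension, the only by-visit antibody summary that the SAP spells out is the ill-fitting one in 6.7.2.

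**Working it through.** The plan states no figure on this point, so there is none to reproduce. The check has three parts.

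**1. Percentage change with a negative coded 0**

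Inputs: N = 50 (SAP 3.3). Everything else is assumed for illustration: negative = 0, positive = 1; baseline positives b = 0, 2 or 5, all staying positive; seroconverters s = 2, 5 or 10.

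- Percentage change = 100 × (post − base) / base. For a seroconverter this is 100 × (1 − 0) / 0, which is undefined. Evaluable subjects = b.
- Absolute change = post − base. It is defined for all 50, with mean s / 50.
- Percentage positive goes from b / 50 to (b + s) / 50.

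| b | s | Evaluable for % change | Seroconverters in % change | Mean absolute change | % positive, baseline to post |
|---|---|---|---|---|---|
| 0 | 2 | 0 | 0 | 0.04 | 0 to 4 |
| 0 | 5 | 0 | 0 | 0.10 | 0 to 10 |
| 0 | 10 | 0 | 0 | 0.20 | 0 to 20 |
| 2 | 2 | 2 | 0 | 0.04 | 4 to 8 |
| 2 | 5 | 2 | 0 | 0.10 | 4 to 14 |
| 2 | 10 | 2 | 0 | 0.20 | 4 to 24 |
| 5 | 2 | 5 | 0 | 0.04 | 10 to 14 |
| 5 | 5 | 5 | 0 | 0.10 | 10 to 20 |
| 5 | 10 | 5 | 0 | 0.20 | 10 to 30 |

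In all nine cases no seroconverter enters the percentage-change summary, and it rests on 0 to 5 of 50 subjects. The absolute-change summary keeps every seroconverter, and its mean is simply the net proportion converting.

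**2. Percentage change with a negative set to a non-zero floor f**

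For a seroconverter with later value p, percentage change is X = 100 × (p / f − 1). With half the floor it is 100 × (2p / f − 1) = 2X + 100. The same subject's change more than doubles with a coding choice that neither document states.

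**3. Visits covered by the n (%) table**

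- Scheduled on treatment (Protocol 6.2.3 and Tables 6-1 to 6-3): Weeks 24, 40 and 52; Months 18, 24, 30 and 36; Months 42, 48, 54, 60, 66 and 72; End of Treatment.
- Named in SAP 6.8.4.5 after baseline: Week 24, Week 40, EOT.
- Not named: Week 52 plus ten extension draws through Month 72 = 11.

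SAP 5.1 defines EOT as the last available on-treatment value. One of the eleven draws can therefore supply a subject's EOT result, but the others do not appear in that table. A subject positive only at unlisted visits and negative at EOT is missed there. The listed visits would suit a 12-month study ending at Week 52, and the SAP introduction still describes the study that way; that this explains the list is an inference.

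**The case against.** The strongest reply is that SAP 6.8.4.5 already reports the right quantity. A reader who looked only at 6.7.2 might infer that seroconverters vanish from the antibody reporting altogether. The documents do not support that reading. The n (%) table counts anyone positive at Week 24, Week 40 or EOT; the absolute-change half of 6.7.2 can be computed for baseline-negative subjects under a 0/1 coding; and SAP 6.8.2 puts all laboratory data in listings. This part of the reply stands and limits the point to the percentage-change half and the missing visits.

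A second reply is that the assay may be graded. The rationale in the protocol's summary of changes says "Low levels of detectable antibody tend to be variable and of no known clinical significance", so a quantitative result cannot be excluded, and the table shells are in a separate document. This also stands in part: that no seroconverter has a percentage change is conditional on a negative being 0 or purely categorical. It does not rescue the rule, because with a floor the result depends on a value that the plan does not give.

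A third reply is that SAP 6.8.4 says other by-visit safety findings will be handled much like laboratory variables. That is general wording. It gives no negative/positive shift for antibodies, and 6.8.4.5 then names its own shorter list of time points. Marginal percentages also do not separate new positives from persistent ones.

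Finally, this is one descriptive analysis in a study with no formal testing. That is correct and is reflected in the grading.

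**Conclusion.** The point holds as a minor specification error. SAP 6.7.2 prescribes a summary that does not suit a positive/negative result and conflicts with the SAP's own rule for categorical variables. Under zero coding, the percentage-change part excludes all baseline-negative subjects; with an assumed 0 to 5 baseline positives of 50, it rests on 0 to 5 subjects. Under a floor, its size is arbitrary.

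The practical gap is by visit: eleven scheduled draws through Month 72 have no suitable antibody summary, so positivity that comes and goes between Week 40 and EOT is not tabulated. How many subjects this affects cannot be judged, since the documents give no antibody rates. SAP 5.3.2 takes baseline from the earlier study for those who completed REPLACE or RELAY, which makes a largely negative baseline plausible, but that is inference. Sample size and the responder endpoint are unaffected.

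**What to change.** 1. In SAP 6.7.2, remove antibodies from the change and percentage-change paragraph and refer to 6.8.4.5.
2. In SAP 6.8.4.5, extend the table to every scheduled antibody visit, including Week 52 and each six-monthly extension draw, with EOT kept as a separate row. Present it as a shift: negative or positive at baseline by negative or positive at the visit, with the number tested, for PTH and ECP separately.
3. Add the number of baseline-negative subjects ever positive on treatment, with the number of baseline-negative subjects tested on treatment as denominator.
4. If titres were recorded, summarize them separately among positives, stating the unit and detection limit.

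The shift table still meets the protocol's endpoint of change from baseline in PTH antibodies, in a form that suits the data. The cost is a short text edit in two SAP sections and one revised table shell; the samples are already in the schedule, so no new data are needed.

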6.7.3. Subset Analyses

Subgroup analyses will be done as specified in Section 7.9.

6.7.4. Exploratory Analyses

There is no exploratory analysis planned.

6.7.5. Sensitivity Analyses

There is no sensitivity analysis planned for this study.

6.8. Analysis of Safety

All safety analyses will be performed on the Safety Population. All values presented in summaries will be observed values. No formal statistical comparisons are planned.

6.8.1. Adverse Events

Adverse events will be coded using MedDRA Version 13.0. Adverse event listings will provide the verbatim term as well as SOC and PT for each recorded event. A separate listing may be produced to provide the SOC, high level term, PT, and lower level term that are associated with each verbatim term.

Treatment emergent adverse events (TEAEs) are defined as AEs whose onset occurs, severity worsens or intensity increases after receiving the study medication of this study and ≤ 30 days after last dose of study drug. If any AE records contain only partial dates, these will be handled by imputation, as described in Section 7.4.3. AEs which are not treatment emergent will be flagged in listings.

An overview of TEAEs will be summarized using the number and percentage of subjects. The number of events will also be presented except for summaries by highest category. Categories summarized will include any TEAEs, severity of TEAEs (any and highest category), relationship of TEAEs to treatment (any and highest category), treatment emergent serious AEs (TESAEs), severity of TESAEs, relationship of TESAEs to treatment, TEAEs leading to discontinuation, and TEAEs leading to death.

Treatment emergent AEs will be summarized using number and percentage of subjects. Subject incidence for AEs within each SOC and PT will be presented, and the number of events will also be summarized except for summaries by highest category. Categories summarized will be the same as those summarized overall, except that no summary table will be provided for TEAEs leading to death.

Summaries of TEAEs and TESAEs will also be presented by PT. These presentations will be sorted by descending incidence.

Listings will be provided for serious adverse events (SAEs), AEs leading to discontinuation, and AEs leading to deaths.

The incidence of hypocalcemia and hypercalcemia will be identified by clinical preview. Prevalence of hypocalcemia and hypercalcemia will be assessed at all visits on the date of visit. The number of subjects with hypocalcemia and hypercalcemia and the number of episodes of hypocalcemia and hypercalcemia will be assessed for the overall trial.

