### 3.2 Study Duration

The duration of the study was originally intended to be about 1 year. The study has been extended to up to 80 months of treatment with a 4-week follow up call/visit. Therefore, the overall duration of the study is expected to be approximately 81 months.

Study visits will be conducted every 2 months and will continue until the subject voluntarily withdraws or until termination of the study. See Section 6.2 for additional follow-up for subjects who develop antibodies specific to PTH. See Table 6-4 for additional follow-up for subjects who develop antibodies specific to PTH.

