#### **4.4 Subject Withdrawal Criteria**

All subjects are free to withdraw from participation in this study at any time, for any reason, specified or unspecified without prejudice to subsequent care. Withdrawn dosed subjects will not be replaced. A subject may be withdrawn from the study under any of the following circumstances:

- Withdrawal of informed consent
- If, in the opinion of the investigator, Institutional Review Board/Independent Ethics Committee/Research Ethics Board (IRB/IEC/REB), Health Authority and/or Shire, it is no longer in the subject's best interest to continue in the study
- Subject no longer meets all inclusion criteria or meets any criterion for exclusion
- Lack of compliance with study procedures or study drug administration, as determined by the investigator
- Occurrence of an SAE determined by the investigator to be possibly related to study drug and not alleviated with treatment of symptoms
- Adverse event
- Hypersensitivity determined by the investigator to be possibly related to study drug
- Pregnancy or lactation
- Administrative reasons
- Treatment with commercial drug (Natpara)

In all cases, the reason for withdrawal must be recorded in the subject's medical records. If the reason is not known, the subject must be followed up to establish whether the reason was an AE and, if so, this must be reported in accordance with the procedures described in Section [6.2.1](#).

As far as possible, all examinations scheduled for the end-of-study evaluations must be performed on all subjects who participate but do not complete the study according to protocol.

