3.3. Determination of Sample Size

Approximately 50 subjects are anticipated to be enrolled. This sample size is based on an estimate of the number of subjects who potentially could roll over from RELAY and/or REPLACE study and is not calculated based on the statistical assumptions.

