6.6. Extent of Exposure

6.6.1. Exposure during this (RACE) study

The extent of exposure is defined as the number of days on treatment, calculated as:
(date of last dose - date of first dose) + 1.

The date of the first dose is based on CRF entry. The date of the last dose will be based on information collected in the paper diary. The extent of exposure and the number of days that the dose was administered will be summarized. The extent of exposure will also be categorized into weeks (<1, 1-<4, 4-<8, 8-<16, 16-<24, 24-<32, 32-<40, 40-<48, 48-<52, ≥ 52) and tabulated. Exposure summaries will be presented for the Safety Population. Number of subjects at different dose level at EOT will be summarized as specified in section 8.7.2.

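### AEs are summarized as subject percentages and event counts with no person-time denominator and almost no split by period, although follow-up may run from days to about 80 months

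*SAP*

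**What the plan says.** **AE measures.** SAP 6.8.1 states: "Treatment emergent AEs will be summarized using number and percentage of subjects". It adds the number of events, overall and by system organ class and preferred term, except in tables that use the highest severity or relationship category. For hypocalcemia and hypercalcemia it also plans prevalence on each visit date, and counts of subjects and episodes over the whole trial. It has no exposure-adjusted rate, no time-to-first-event estimate and no general AE table by study period.

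**Length of observation.** Protocol 3.2 states: "The study has been extended to up to 80 months of treatment with a 4-week follow up call/visit". At the other end, SAP 6.3 requires only one dose and some follow-up information for the Safety Population. Protocol 4.4 allows withdrawal at any time, lists a move to the commercial product among the reasons, and does not replace dosed subjects. The treatment-emergent window in SAP 6.8.1 runs from the first RACE dose to 30 days after the subject's own last dose, so its length varies by subject.

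**Exposure.** SAP 6.6.1 summarizes exposure in a separate table. It says "The extent of exposure will also be categorized into weeks", and the last category is open from 52 weeks upward.

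**Protocol against SAP.** Protocol 8.2, like the safety paragraph of the synopsis, names AEs among the data to be summarized by time of collection. SAP 3.4.2 says that no protocol analysis is changed.

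**The concern.** The primary objective is long-term safety and tolerability. A cumulative percentage of subjects with an event answers that question only if subjects are followed for similar lengths of time. Here the time may differ greatly between subjects, and the percentage rises with follow-up even when the underlying rate is constant. A high figure may mean that subjects stayed long, and a low one that they left early.

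The effect carries into the two interim reports in SAP 5.5 (data to 31 May 2013 and to 8 May 2017). For a fixed set of subjects, a cumulative percentage can only stay level or rise from one cut to the next, even if the event rate is falling. Whether risk is stable, rising or falling under continued treatment is what a study extended for long-term safety should show.

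**Working it through.** **1. The plan's own figures.** Enrolment is stated as "Approximately 50 subjects are anticipated to be enrolled". It is a roll-over estimate that "is not calculated based on the statistical assumptions", so there is no power or event assumption to reproduce. Duration can be checked: 80 months + 28 days / 30.4375 = 80.9 months, which agrees with the Protocol 3.2 statement that "the overall duration of the study is expected to be approximately 81 months".

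**2. Exposure categories.** 80 months × 30.4375 / 7 = 347.9 weeks. The share of that range above 52 weeks is 1 − 52/347.9 = 85%, and all of it falls in one category.

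**3. Percentage against length of stay.** The documents give no AE or dropout rates, so the rates below are assumptions. With a constant first-event rate L per person-year and everyone followed for t years, the expected percentage is 1 − exp(−Lt).

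| L (assumed) | 12 months | 36 months | 80 months |
|---|---|---|---|
| 0.02 | 2.0% | 5.8% | 12.5% |
| 0.10 | 9.5% | 25.9% | 48.7% |
| 0.50 | 39.3% | 77.7% | 96.4% |

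If half the subjects leave at 24 months and half stay for 80, then at L = 0.10 the result is (18.1% + 48.7%)/2 = 33.4%.

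**4. Percentage against dropout.** Let the dropout hazard be D per year and T = 80/12 = 6.67 years. The expected percentage is L/(L+D) × [1 − exp(−(L+D)T)]. The expected person-years to first event or end of follow-up are 50 × [1 − exp(−(L+D)T)]/(L+D). The 30-day tail after the last dose is ignored. At L = 0.10:

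| D (assumed) | Percentage with an event | Person-years at risk | First events per person-year |
|---|---|---|---|
| 0 | 48.7% | 243.3 | 0.10 |
| 0.05 | 42.1% | 210.7 | 0.10 |
| 0.10 | 36.8% | 184.1 | 0.10 |
| 0.20 | 28.8% | 144.1 | 0.10 |
| 0.40 | 19.3% | 96.4 | 0.10 |

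The percentage more than halves while the rate does not move.

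**5. The reverse reading.** A reported 20% implies L = −ln(0.8)/t. That is 0.223 per year if all were followed for 12 months, 0.074 for 36 months and 0.034 for 80 months, a range of 80/12 = 6.7-fold.

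**6. Choice of remedy.** First-event rates by year would fail for common categories, because subjects leave the risk set at their first event. If the rate for any TEAE were 1 to 3 per year (assumed), the number of 50 subjects still at risk after one year would be 50·exp(−1) = 18.4 down to 50·exp(−3) = 2.5, even without dropout. The split by period therefore has to count all events.

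**The case against.** The strongest reply is that the plan offers more than percentages. Event counts are planned overall and by term, and exposure is summarized on the same Safety Population. A reader could multiply mean exposure by the number of subjects and obtain a rough overall event rate. This stands, and a claim that AEs are reported only as crude percentages would be wrong. The rough rate still gives neither first-event incidence nor change over time, because events are not tabulated by period.

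Hypocalcemia and hypercalcemia do get a by-visit view. That counts what is present on the visit date, and extension visits are two months apart. Their episode counts are for the whole trial.

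It can also be said that the study has one arm and that "No formal statistical testing will be conducted for this study". This stands too: no treatment comparison is biased, and the harm is to interpretation. A confidence interval on a rate is not a test and fits a descriptive plan.

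Three other inferences are tempting but are not supported:

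- That some subjects did have only days of follow-up. The population definition and the exposure category below one week allow it, but no follow-up distribution is given.
- That the AE method is a leftover from a 12-month plan. SAP 1 still describes a 12-month study and SAP Appendix I lists no AE change, but SAP version 1.0 is not available to confirm it.
- That a planned comparison with the parent studies is spoiled. No such AE comparison is planned here.

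**Conclusion.** The point holds. SAP 6.8.1 has no person-time denominator and, apart from by-visit hypocalcemia and hypercalcemia prevalence, no split by period. It also leaves undone the time-based AE summary in Protocol 8.2, although SAP 3.4.2 reports no change. A reader might infer that no time-based AE summary was ever intended. Protocol 8.2 shows otherwise, and the gap lies in the SAP.

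The size depends on rates that the documents do not give. At an assumed constant 0.10 per person-year, the percentage runs from 9.5% at 12 months to 48.7% at 80, or from 48.7% to 19.3% as the dropout hazard goes from 0 to 0.40 per year. The direction does not depend on the rate chosen. The figures assume constant hazards and dropout unrelated to risk. Rates by interval relax the first assumption. They do not remove selective dropout, but they show how many subjects each interval rests on.

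**What to change.** Keep the current tables. Add the following to SAP 6.8.1 for any TEAE, TESAEs, hypocalcemia, hypercalcemia and TEAEs leading to discontinuation:

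- (a) All events per 100 patient-years, overall and by 12-month interval, among subjects still followed, with the number of subjects and the person-years shown for each interval.
- (b) Overall first-event incidence per 100 patient-years at risk with a 95% confidence interval. Time at risk should match the treatment-emergent window: first RACE dose to last dose plus 30 days, ending at the first event.

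In addition, (c) extend the exposure categories in SAP 6.6.1 beyond 52 weeks.

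Item (a) would also supply a time-based AE summary for these categories, as Protocol 8.2 foresees. If the sponsor does not want one, SAP 3.4.2 should record the departure.

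The cost is a few extra table columns. AE onset dates and first and last dose dates are already collected. Late intervals will be sparse: at an assumed dropout hazard of 0.20 per year, about 50·exp(−0.20 × 5) = 18 subjects would remain at 60 months. That is why the denominators need to be shown.
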